## 12.0 Provisions to Monitor the Data to Ensure the Safety of Subjects

*Sources of Material:* Forty-five individuals will be enrolled in the current project. The assessments will be collected only after obtaining informed consent, and for research purposes only. These records will be kept by [name] in password protected confidential electronic files with restricted access.

*Confidentiality Procedures:* As the PI, [name] will assure all procedures protecting study data designed to guard subject confidentiality conform to the MUSC Research Protection Program requirements. Additionally, the MUSC IRB must approve all procedures before the study can begin. All data will be stored securely in locked offices or laboratories accessible only by study staff. Further, all information that could potentially identify a subject directly is removed from all study data. This will be replaced with a unique identifier code. The key to linking the code to subject identity will be kept

separately from study data, in a locked file. Only study staff involved in clinical recruitment and assessment will have access to individually identifiable private information. All other study staff will only have access to the coded identifier.

**Adverse Events:**

Given that this is a very low risk study assessing a behavioral intervention and a medication (nicotine patches and lozenges) that is so safe it has been available over-the-counter since 1996, we do not expect serious adverse events. Please see section 14 "Risks to Subjects" for more research on the safety of NRT, augmented doses of NRT, and NRT for vaping cessation.

**Adverse Events:**

Participants will have the phone numbers of the PI [name] [contact]) and will be prompted to contact her if an adverse event occurs. If a participant contacts the research team due to an adverse event, the event will be appropriately addressed, and the event will be reported per the IRB standard procedures and criteria below. Adverse events will also be tracked via daily and monthly assessments, where they will be able to rate the incident as mild, moderate, or severe. The research staff, with the guidance of [name] and [name] will track the relatedness of the incident to study medication. The variables that we will encourage the pharmacist and PI to assess include severe reports of the following symptoms (listed symptoms of nicotine overdose per package insert): nausea, salivation, abdominal pain, sweating, headache, diarrhea, dizziness and weakness. We will determine if any adverse events result in dropouts or are serious according to FDA guidelines. Following the report of an adverse event and consultation with [name], the participant will be contacted to discuss modifying their NRT usage.

Adverse events will be defined and graded for risk as follows:

**Coding of Severity:**

- 0 = No adverse event or within normal limits
- 1 = Mild adverse event
- 2 = Moderate adverse event
- 3 = Severe, resulting in psychiatric or medical hospitalization
- 4 = Life-threatening adverse event
- 5 = Fatal adverse event

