### 4.0 Study Endpoints.

#### Primary Endpoint:

*Days of dual use abstinence (Day 28, Day 56):* The primary outcome of interest is the number of days participants self-report abstinence from both e-cigarettes and smoking. These data will be derived from daily surveys that query about the previous day's e-cigarette use (yes/no, estimated number of times

vaped, estimated amount of cartridge/refill used) and cigarette smoking (yes/no overall, number of cigarettes smoked). Non-responders and missing data will be coded as not abstinent.

Secondary Endpoints:

**Reduction (Day 28, Day 56):** In addition to number of days of complete dual product abstinence, we will use baseline and daily survey data (described above) to calculate the reduction of e-cigarette use and smoking between groups from baseline to end of treatment.

**Safety (Day 28):** To further assess differences in acceptability and response to the treatment doses, adverse events between groups will be evaluated. NRT side effects will be captured during daily diary assessments using the Systematic Assessment for Treatment Emergent Events (SAFTEE).

**Feasibility/Acceptability (Day 28):** Feasibility and acceptability endpoints will be determined by the proportion of eligible subjects able to be contacted who subsequently enroll, the proportion of enrolled subjects who complete the Day 28 survey, and the proportion of enrolled subjects who complete ≥80% of their daily surveys during the treatment period. Participants will report satisfaction and helpfulness of the intervention at the end of treatment (Day 28).

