**Coding of Attribution will be made for adverse events grade 3 and above (ie, serious adverse events):**

- 1 = Unrelated to study interventions
- 2 = Unlikely relationship to study interventions
- 3 = Possible relationship to study interventions
- 4 = Probable relationship to study interventions
- 5 = Definite relationship to study interventions

The FDA's definition of serious adverse events (21 CFR 312) will be used. Serious Adverse Events include any untoward medical occurrence that at any dose results in death or the immediate risk of death, hospitalization, or the prolonging of an existing hospitalization, persistent or significant disability/incapacity or a congenital anomaly/birth defect, new cancer, or medication overdose.

Serious adverse events, whether unanticipated or anticipated, will be reported immediately (within 24 hours) to the MUSC Institutional Review Board. The PI will evaluate the adverse event and determine whether the adverse event affects the Risk/Benefit ratio of the study and whether modifications to the protocol or the consent procedures are required.

Unanticipated problems involving risk to subjects or others (defined as an event that is 1] unexpected, 2] related or possibly related and 3] serious) will be reported to the IRB no later than 10 working days after the event or notification to the research team that the event has occurred. The reported information will include: a description of the event, the date of occurrence, whether it is a local or outside report, how the event affected the rights, safety or welfare of the subject or others, current status of MUSC subjects, and any planned changes or modifications to the project as a result of the event.

Any participants' experiences of unanticipated adverse events will be reported on an annual basis to the MUSC Institutional Review Board.

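### The only severe grade requires hospitalisation and is treated as the same thing as a serious event, so a severe adverse event without admission fits no grade on the protocol's own scale

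*Combined protocol and SAP*

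**What the plan says.** Four pieces of text bear on this.

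- **Participant rating (Section 12.0, Adverse Events).** Events are followed in daily and monthly assessments. Of participants it says "they will be able to rate the incident as mild, moderate, or severe". No admission condition is attached. The same paragraph directs the pharmacist and the investigator to severe reports of symptoms listed for nicotine overdose, such as nausea, dizziness and weakness. It also says that staff follow whether the incident is related to study medication, with no severity threshold and no scale.
- **Staff grade (Section 12.0, Coding of Severity).** The scale runs from 0 to 5. The three levels that matter here are "2 = Moderate adverse event", "3 = Severe, resulting in psychiatric or medical hospitalization" and "4 = Life-threatening adverse event".
- **Attribution (Section 12.0, Coding of Attribution).** The five-level relatedness code is introduced with "Coding of Attribution will be made for adverse events grade 3 and above (ie, serious adverse events". The definition of a serious event that follows includes death or immediate risk of it, hospitalisation or its prolongation, lasting or significant disability and birth defect, and ends with "new cancer, or medication overdose".
- **Use of the data (Section 4.0, Safety).** As a secondary endpoint, "adverse events between groups will be evaluated", with side effects captured by SAFTEE in the daily diary. Section 14.0, items 2.3 and 2.4, repeats the intention to compare safety between the dose arms.

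**The concern.** Severity (how intense an event is) and seriousness (what it leads to) are different properties, and grade 3 merges them. The events caught in between are the ones this trial most needs to grade well. Section 14.0, item 2.3, reports that some high-dose studies showed more non-serious effects such as nausea, dizziness and headache, while high-dose studies did not show more serious ones. Section 12.0 itself expects no serious events. If the augmented arms are less well tolerated, the signal should therefore appear mainly among events without admission, where the scale has no severe level.

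The aims (Section 1.0) name the best tolerated dose as something the study should inform for a later trial. With 15 participants per arm, a scale that places severe events in the wrong category wastes information that is already scarce.

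**Working it through.** No arithmetic applies. The check is to take events that the protocol foresees and apply its rules as written.

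**Event 1: intense nausea that the participant rates severe, with no admission, no threat to life, and not judged an overdose.**
- Grade 4 fails, because life is not threatened.
- Grade 3 fails, because there is no hospitalisation.
- Grade 2 fails, because it means moderate.
- No grade matches. Coding it 2 understates the intensity. Coding it 3 contradicts the wording of grade 3 and brings in the label of serious, which carries reporting to the IRB within 24 hours.
- Attribution: below grade 3 and not serious, so the five-level code is not required. The Adverse Events paragraph still calls for relatedness to be followed, on a scale that is not given.

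**Event 2: the same event, now judged a medication overdose, still without admission.**
- Serious, because overdose is on the protocol's own list.
- Grade 3 still fails on hospitalisation.
- Attribution: the grade threshold says no code, and the parenthesis equating that threshold with serious events says code it. The two halves of one sentence give different answers.

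**Event 3: a new cancer or a significant disability that comes to light without admission or immediate threat to life.**
- Serious by definition, yet not grade 3, 4 or 5. The attribution sentence conflicts with itself as in event 2.

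**Relation between the two classes.** Grade 3 (hospitalised), grade 4 (life-threatening) and grade 5 (fatal) all meet the definition of serious, so every event at grade 3 or above is serious. The reverse is false: events 2 and 3 are serious and fall outside grades 3 to 5. The equation in the attribution rule therefore holds in one direction only.

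**Why attribution of every serious event is needed.** The definition of an unanticipated problem later in Section 12.0 requires an event to be unexpected, serious and at least possibly related. That judgement cannot be made for a serious event that has no relatedness assessment.

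**What does not pass through the 0 to 5 scale.** The Safety endpoint in Section 4.0 names adverse events and SAFTEE, and mentions neither the grades nor the attribution code. Nothing in Section 12.0 says that the staff grade replaces the participant's rating.

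**The case against.** The strongest reply is that little is lost in practice. The 0 to 5 scale sits in the monitoring and reporting section and is introduced as a grading for risk, not as an endpoint measure. The safety comparison can use SAFTEE and participant ratings. Seriousness is already judged separately, since Section 12.0 says that the team will decide whether events are serious under FDA guidelines, and overdose, disability and new cancer are reportable whatever their grade. The two relatedness statements can be read together as general tracking for all incidents and a formal code for serious ones. Severe nicotine-excess symptoms are assessed by the pharmacist and the investigator in any case, and an endorsed side effect leads to staff contact (Section 14.0, item 2; Section 16.0).

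Most of this stands, and it limits the consequences. It leaves the defect in place: grade 3 still excludes a severe event without admission, and the attribution sentence still equates two classes that differ. Reading the relatedness statements together also leaves non-serious events with tracking but no categories to record it in. It is fair, too, that five-level attribution of every event goes beyond the minimum repair, and the fix treats that part as a preference.

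**Conclusion.** The grading rule is wrong as written and should be corrected before adverse events are coded. Every severe event without admission and without threat to life lacks a matching grade, and serious events can fall outside grades 3 to 5. The documents give no rate for such events, so no count by arm can be stated. If staff down-code, a table of staff grades will show too few severe events. If they code 3, it will show events as serious that are not. If practice varies, it will show a mixture.

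Three stronger readings are tempting, and the documents support none of them.

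- A reader might infer that the arms cannot be compared on severe events. They can, from participant ratings and SAFTEE.
- A reader might infer that relatedness goes unrecorded below grade 3. Section 12.0 promises to track it without a threshold. What is missing is a defined scale for events that are not serious. No comparison of treatment-related events by arm is planned, so none is lost.
- A reader might infer that serious events would go unreported. The definition and the 24-hour rule apply whatever the grade.

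The conclusion rests on reading grade 3 literally, with hospitalisation as part of its definition, and on participants' ratings being kept alongside the staff grade.

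**What to change.** Reconcile the three parts of Section 12.0 (Adverse Events, Coding of Severity, Coding of Attribution):

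1. Define grades 1 to 3 by intensity alone, as mild, moderate and severe, and remove the hospitalisation condition from grade 3. Grades 4 and 5 can stay.
2. Record seriousness as a separate yes/no item under the 21 CFR 312 definition already given.
3. Delete the equation of grade 3 and above with serious events. It would be false in both directions once step 1 is made.
4. Apply the existing 1 to 5 attribution code at least to all serious events whatever their grade and to all severe events. Preferably apply it to every event, since relatedness is already to be tracked.
5. State that the participant's rating is kept beside the staff grade, and which of the two is used when severity is reported by arm.

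The cost is a change to the adverse event form and the protocol wording, plus a little staff time for coding. Sample size, visits, dosing and the primary analysis are unaffected.

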**Coding of Attribution will be made for adverse events grade 3 and above (ie, serious adverse events):**

- 1 = Unrelated to study interventions
- 2 = Unlikely relationship to study interventions
- 3 = Possible relationship to study interventions
- 4 = Probable relationship to study interventions
- 5 = Definite relationship to study interventions

The FDA's definition of serious adverse events (21 CFR 312) will be used. Serious Adverse Events include any untoward medical occurrence that at any dose results in death or the immediate risk of death, hospitalization, or the prolonging of an existing hospitalization, persistent or significant disability/incapacity or a congenital anomaly/birth defect, new cancer, or medication overdose.

Serious adverse events, whether unanticipated or anticipated, will be reported immediately (within 24 hours) to the MUSC Institutional Review Board. The PI will evaluate the adverse event and determine whether the adverse event affects the Risk/Benefit ratio of the study and whether modifications to the protocol or the consent procedures are required.

Unanticipated problems involving risk to subjects or others (defined as an event that is 1] unexpected, 2] related or possibly related and 3] serious) will be reported to the IRB no later than 10 working days after the event or notification to the research team that the event has occurred. The reported information will include: a description of the event, the date of occurrence, whether it is a local or outside report, how the event affected the rights, safety or welfare of the subject or others, current status of MUSC subjects, and any planned changes or modifications to the project as a result of the event.

Any participants' experiences of unanticipated adverse events will be reported on an annual basis to the MUSC Institutional Review Board.

## **14.0 Risks to Subjects**

The main study procedures include completion of questionnaires and using NRT, both of which are generally considered minimal risk procedures. Although these procedures do carry slight risk, the primary risks of the study is loss of confidentiality. There is also a risk that the treatment the study participant is randomized to may prove to be less effective than the other study treatment or other available treatments.

1. Breach of confidentiality: There is the potential risk of breach of confidentiality of laboratory information. The Co-PIs have experience as an investigator dealing with such sensitive information and has experience assuring that data is adequately protected. Safeguards to protect confidentiality include locked records and firewalls around password-protected electronic data, and all study data being coded, with the key linking the code with a subject's identity being kept in a separate, locked file.
2. NRT

Daily diary surveys will monitor for AEs related to the NRT. If a participant endorses an adverse side effect, they will be contacted by research staff to determine the degree of the event and make recommendations regarding continuing product use as recommended by the TTP Clinical Pharmacist [name]. These will be recorded as a part of the study file.

2.1 Nicotine patches and lozenges: Exclusion criteria will include endorsement of history of any of the following medical conditions that are contraindicated for patch use: myocardial infarction, arrhythmias, angina, vascular disease, or medical conditions in which consumption of phenylalanine is contraindicated.

The most common side effects from nicotine patch are skin irritation, insomnia, and headache or nausea. Nicotine lozenges may cause side effects, including sore throat, indigestion, gas, and nausea.

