## **5.0 Study Population / Inclusion and Exclusion Criteria**

We aim to recruit 45 participants (15 in each group: A, B, and C). Inclusion criteria include: 1) age 18+; 2) daily nicotine-containing e-cigarette user (25+ days per previous month); 3) e-cigarette use 5+ times/day; 4) e-cigarette use > 1 year; 5) smoking >1 cigarette on 5-7 days per week 6) interest in quitting smoking and e-cigarette within the next month (>7 on 10-point scale); 7) willingness to use NRT; 8) able to receive text messages/email, and 8) mailing address in SC.

Exclusion criteria includes medical conditions contraindicated to NRT use (including pregnancy, past month myocardial infarction, current cardiac arrhythmia, current angina, uncontrolled vascular disease, or medical conditions in which consumption of phenylalanine is contraindicated, including Phenylketonuria [PKU] and allergy to phenylalanine), individuals reporting current use of other nicotine-containing products and/or smoking cessation medications, those who vape non-nicotine substances, and individuals unable to consent (e.g. significant cognitive deficit, non-English speaking). These criteria were used in the proof-of-concept study which recruited at an acceptable pace. Exclusion criteria, including health information, will be ascertained via self-report on the online pre-screener. We have requested a waiver of signed consent for this assessment.

Pregnancy status will be ascertained via self-report on the online pre-screener. In addition, we will ask participants if they are sexually active and if they are using any type of contraceptive method (with a list of available options). If female participants are deemed eligible (i.e., not pregnant and not engaging in unprotected sex) and schedule an intake, they will be mailed a pregnancy test. They will be told they will not complete the test until after they have consented to the study and agree to continue. During consent, discuss the exclusion criteria for pregnancy, as well as review risks of medication use as it pertains to pregnancy. Following consent, during the initial intake assessment, we will conduct the pregnancy test. The participant will perform the pregnancy test at home and report results to the research staff via sending a photo of the test (if doing consent over phone) or showing the test on video (if consenting via video call). If the test is negative, we will continue with the rest of the study procedures.

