## **10.0 Study Design / Methods**

A target of 45 dual users across South Carolina will be recruited through various media outlets. Advertising will solicit vapers motivated to quit. Dual users will consent to be screened online for study eligibility, including potential for pregnancy. Pregnancy status and health conditions contraindicated to NRT (past month myocardial infarction, current cardiac arrhythmia, current angina, uncontrolled vascular disease, or medical conditions in which consumption of phenylalanine is contraindicated, including Phenylketonuria [PKU] and allergy to phenylalanine) will be ascertained via self-report on the online pre-screener. In addition, we will ask participants if they are sexually active and if they are using any type of contraceptive method (with a list of available options). If female participants are deemed eligible (i.e., not pregnant and not engaging in unprotected sex) and schedule an intake, they will be mailed a pregnancy test. They will be told they will not complete the test until after they have consented to the study and agree to continue. During consent, we will discuss the exclusion criteria for pregnancy, as well as review risks of medication use as it pertains to pregnancy and the aforementioned medical conditions.

If the participant qualifies, research staff will schedule a time to complete the interview and baseline assessment battery. Following consent, during the initial intake assessment, we will conduct the pregnancy test on applicable participants. If the test is negative, we will continue with the rest of the study procedures. Participants will then be randomized to study arm (Arm A (21mg patch, qd + 4mg lozenge prn [minimum of 5 & up to 20 per day]); Arm B (21mg patch + 14mg patch qd + 4mg lozenge prn [minimum of 5 & up to 30 per day]), or Arm C (2X21mg patches qd + 4mg lozenges prn [minimum of 5 & up to 40 per day]). Participants will be provided with a 28-day supply of NRT by mail and a self-help booklet (which includes instructions for medication use) and instructions to select a target quit date within 1 week. Research staff will contact the participants upon receipt of the materials and obtain the

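### The cardiovascular exclusions are stated in two incompatible ways: Sections 5.0 and 10.0 limit them to recent, current or uncontrolled disease, while Section 14.0 excludes any history

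*Combined protocol and SAP*

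**What the plan says.** The combined protocol and SAP states the cardiovascular exclusions three times.

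- Section 5.0 (Study Population / Inclusion and Exclusion Criteria) lists, among the conditions that rule out nicotine replacement therapy (NRT), "past month myocardial infarction, current cardiac arrhythmia, current angina, uncontrolled vascular disease". On how they are established it says: "Exclusion criteria, including health information, will be ascertained via self-report on the online pre-screener".
- Section 10.0 (Study Design / Methods) repeats that list as "health conditions contraindicated to NRT (past month myocardial infarction, current cardiac arrhythmia, current angina, uncontrolled vascular disease" and says in the same sentence that self-report on the pre-screener is how they are ascertained. It adds that the consent discussion will review medication risks in relation to these conditions.
- Section 14.0 (Risks to Subjects), item 2.1, says: "Exclusion criteria will include endorsement of history of any of the following medical conditions that are contraindicated for patch use". The list that follows is "myocardial infarction, arrhythmias, angina, vascular disease, or medical conditions in which consumption of phenylalanine is contraindicated".

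No section says which statement governs, and none explains the difference.

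**The concern.** Section 14.0 does more than leave out the qualifiers. It puts a history criterion in their place and words it as an exclusion rule that depends on what the participant endorses. Staff cannot follow both versions for a person with past or controlled cardiovascular disease.

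What is at stake is how well the description of participant protection matches what is done. Under Section 7.0 the study is run entirely remotely, and the documents describe no examination, ECG or record check at entry. The entry questions therefore carry most of the cardiac safeguard. Arms B and C receive augmented doses, and Section 14.0, item 2.3, acknowledges that participants may be given a schedule above the labelled one. The adverse-event text in Section 12.0 sends the reader to Section 14.0 for NRT safety. Someone judging risk from that section would believe that people with any such history are kept out.

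**Working it through.** No sample size, rate or power figure enters this point, so there is nothing to compute. The check sets the three statements side by side and applies each to the same otherwise eligible people.

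| Condition | Sections 5.0 and 10.0 | Section 14.0, item 2.1 | Case that separates them |
|---|---|---|---|
| Myocardial infarction | within the past month | any history | infarction more than one month ago |
| Arrhythmia | current | any history | past, not current |
| Angina | current | any history | past, not current |
| Vascular disease | uncontrolled | any history | controlled |

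1. None of the four separating cases meets a cardiovascular exclusion listed in Section 5.0 or 10.0.
2. All four are excluded under Section 14.0, item 2.1. The conflict therefore covers every cardiovascular item (4 of 4).
3. The conflict runs one way. Anyone excluded on cardiovascular grounds by Sections 5.0 and 10.0 is also excluded by Section 14.0, but not the reverse. Section 14.0 is strictly the broader exclusion.
4. The phenylalanine item agrees in substance in all three places and is not part of the problem.
5. Could Section 5.0 be read as an open list, since it introduces its conditions as examples? That would leave its limits on time and status with no effect, and Section 10.0 gives the same cardiovascular conditions without such an introduction. The conflict remains.
6. Do the lists serve different purposes? Sections 5.0 and 10.0 refer to conditions that rule out NRT, and Section 14.0 to conditions that rule out the patch. Every arm receives patches, so both apply to every participant.

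**The case against.** The strongest reply is that the operating rule can be read from the text. Section 5.0 is the formal eligibility section. Section 10.0 ties the limited list to the pre-screener and to the consent discussion. Section 14.0, item 2.1, is one sentence in a risk narrative and is visibly abbreviated: it leaves out pregnancy, which is handled later in that section, and does not name phenylketonuria. It may be a loose paraphrase that lost its qualifiers. Section 8.0 also provides a staff appointment to confirm eligibility before consent, and Section 14.0 provides daily side-effect monitoring with pharmacist input.

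Much of this stands. A reader might infer that nobody can tell which list the pre-screener will use, or that an unattended survey is the only check. The documents support neither: Section 10.0 points to the limited list, and Section 8.0 adds the appointment. A reader might also infer that the safety comparison between arms is biased. It is not, because either list is applied before randomisation and equally to all arms; only the population described would change.

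The reply does not remove the contradiction. If Sections 5.0 and 10.0 are the working rule, Section 14.0 misstates the protection offered. If Section 14.0 is the intended rule, the screening described in Section 10.0 does not deliver it. The paraphrase reading is plausible, but the documents do not confirm it.

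**Conclusion.** The point holds as an internal inconsistency in a safety exclusion, and it should be corrected. All four cardiovascular conditions are affected, and in each a definable group is admitted by two sections and excluded by a third.

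The number of people concerned cannot be derived, because the documents give no prevalence of past or controlled cardiovascular disease among dual users; it could be zero. A reader might try to size the point by noting that one such enrolment would be 1 of 15 in an arm. That describes a hypothetical enrolment and would be true of any criterion, so it is not evidence of magnitude.

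The primary analysis, the randomised comparison and the power statement are untouched. The conclusion assumes only that the three sections mean what they say. It takes no position on which exclusion is clinically right.

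**What to change.** Reconcile Sections 5.0, 10.0 and 14.0 (item 2.1) into one identical list, with one time frame or status stated for each condition. Then check that the pre-screener items, the eligibility confirmation appointment in Section 8.0 and the consent discussion all use that list. The investigator and the clinical pharmacist decide which wording applies.

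The cost is a protocol wording amendment with IRB approval and a check of the screener items. Nothing in the statistical analysis changes.
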